The eligible patient population for the pilot study will be all patients at the two pilot clinics who are age 65 or greater with a diagnosis of Alzheimer's disease and related dementias (ADRD) from either ICD visit codes or documentation on the problem list. Patients must also be taking 5 or more chronic medications, and active patients, defined as having ≥ 1 visit to the primary care clinic within the past year. We will enroll 60 patient-care partner dyads (15 dyads per arm at each site).

STUDY TEAM ROSTER

Principal Investigator:	[name], MPH, PhD Johns Hopkins University School of Medicine [name] [contact] [contact] [contact]
Co-Investigators:	[name], MS Institute for Health Research, Kaiser Permanente Colorado [name] [contact] [contact] [contact] Site Principal Investigator, Kaiser Permanente
	[name], MPH Johns Hopkins University School of Medicine [name] [contact] [contact] [contact] Co-Investigator
	[name] Johns Hopkins Bloomberg School of Public Health [name] [contact] [contact] [contact] Co-Investigator
	[name] Johns Hopkins Center on Aging and Health [name] [contact] [contact] [contact] Co-Investigator, Statistician
	[name], MSPH Institute for Health Research, Kaiser Permanente Colorado

[name] [contact] [contact] [contact] Co-Investigator

PARTICIPATING STUDY SITES

[name], MPH, PhD

Johns Hopkins University School of Medicine [name] [contact] [contact] [contact]

[name], MS

Institute for Health Research, Kaiser Permanente Colorado [name] [contact] [contact] [contact]

1 STUDY OBJECTIVES

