4.2 Exclusion Criteria

Candidates meeting any of the following exclusion criteria at baseline will be excluded from study participation:

- As both the pilot and the planned pragmatic trial will be based in primary care, individuals residing in long term care facilities or enrolled in hospice will be excluded.
- Individuals who cannot converse comfortably in English will be excluded because the FCMAHS has not been validated in other languages.

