 This is the standard approach that clinic staff use to call patients with dementia on the phone and identify their care partners during the course of clinical care. As the intervention is designed to address the needs of care partners and requires their participation, the project assistant will ask to speak with the care partner first. Because some patients with mild or moderate dementia may be interested in hearing about the program, the project assistant will offer to describe it to the patient as well.
- Patients who are unwilling or unable to identify a care partner who helps them manage their medicines will be excluded. The project assistant will document the reasons for ineligibility in a REDCap Screening Log.
- The project assistant will briefly describe the pharmacist consult to the care partner. If the care partner agrees, the project assistant will schedule the pharmacist call, which will occur immediately (within 4 weeks) for the intervention group and at approximately 3 months for the delayed intervention control group.

4) If patients or care partners opt out during the phone call, the project assistant will document the reason (eg, no time to participate, not interested) in a REDCap Screening Log.

5) Dyads randomized to the delayed intervention group will be told that they will receive another phone call from the project assistant in approximately 3 months to remind them of their appointment with the clinical pharmacist.

6) After scheduling the pharmacist consult, project assistants will offer care partners in both groups the option of completing the secondary outcome measure, the Family Caregiver Medication Administration Hassles Scale (FCMAHS). For care partners who are interested in completing the FCMAHS, project assistants will obtain verbal consent when administering the measure over the phone (see script). If the care partner does not wish to complete the FCMAHS over the phone during the scheduling phone call, the project assistant will offer to call back before the pharmacist visit (up to 28 days) or to later e-mail the care partner a link to an electronic version.

5 STUDY INTERVENTIONS

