6.2.4 Completion/Final Evaluation

As described above, there will be one follow up phone call/e-mail to administer the FCMAHS 3 months after enrollment. Care partners who do not wish to complete the FCMAHS by phone will be offered an electronic version and will be e-mailed a link. All

other data will be extracted from the EHR and VDW. If participants discontinue the intervention early (eg, by opting out during the pharmacist phone call), we will still extract their data from the EHR and VDW but will not offer the FCMAHS.

7 SAFETY ASSESSMENTS

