9.2 Sample Size and Randomization

Sample size calculation: With an attrition rate of 10%, a sample size of 30 dyads per arm will produce a 2-sided 95% confidence interval with a width equal to 0.4 standard deviation (SD) when the SD of the study outcome (ie, based on normalized score) is 1.

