9.5 Data Analyses

In Aims 1 and 2a, our focus will be on descriptive statistics (counts and proportions). In Aim 2b, the primary analyses will rely on intention-to-treat analysis to present the comparative results of the trial. All events following randomization will be counted. Analyses using post-randomization data (eg, intervention compliance) will be discussed as secondary analyses. We will distinguish non-compliance with intervention from non-compliance with follow-up (ie, missing data).

For our primary outcome measure, pMRCI, we will first perform correlation analyses between chronic medication count and pMRCI scores at baseline. We will analyze changes in pMRCI before and after intervention and evaluate the impact of intervention assignment on the change scores using linear regression. The cluster by health system effect will be accounted for in the calculation of robust standard errors. Given the pilot nature of this trial, we will focus on estimates of precision in detecting treatment effects that will aid in the planning of a larger, sufficiently powered ePCT. We will also explore treatment effects by gender, age strata and race/ethnicity, again focusing on estimates of with-stratum variabilities instead of statistical significance. We will use multiple imputation to account for missing data.

For our secondary outcome measure, FCMAHS, we will first construct summary scores of the FCMAHS subscales using principal components analysis. We will then analyze changes in FCMAHS before and after intervention and evaluate the impact of intervention assignment on the change scores using linear regression.

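### FCMAHS is to be scored by principal components fitted in the pilot itself, with no statement that one set of weights serves both visits; fixed instrument scores would cost nothing

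*Combined protocol and SAP*

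**What the plan says.** Sections 9.1 and 9.5 carry the same two steps for the FCMAHS: "we will first construct summary scores of the FCMAHS subscales using principal components analysis", and then "evaluate the impact of intervention assignment on the change scores using linear regression". Neither section names published or fixed weights, the number of components to keep, the visit or visits on which the components are fitted, or whether one set of weights applies at baseline and at 3 months.

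Elsewhere the plan treats the scale as an existing instrument. It cites a development paper, refers to subscales, and in section 4.2 excludes people who are not comfortable in English because "the FCMAHS has not been validated in other languages".

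The data are limited. The Précis and section 3 plan 60 dyads, 15 per arm at each of two sites. Under section 4.3 the project assistants "offer care partners in both groups the option of completing the secondary outcome measure", so completion is voluntary. For participants who discontinue early, section 6.2.4 says "we will still extract their data from the EHR and VDW but will not offer the FCMAHS". Section 9.4 lists the 3-month change in FCMAHS among the Aim 2b measures, beside response rate and completion time.

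**The concern.** A score whose weights are estimated from the trial's own data has units that belong to that data set. Aim 2b prepares the FCMAHS as the secondary outcome of the ePCT. An SD or mean change on a pilot-fitted component is useful there only if the ePCT applies the same weights, and nothing in the plan assures this.

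There is also tension between relying on the scale's validation for eligibility and then building its summary score afresh.

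The more concrete risk is the change score. If the components were fitted separately at baseline and at 3 months, the two scores would have different origins and scales, and their difference would not measure change.

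**Working it through.** **1. Number of care partners.** Ceiling: 15 × 2 arms × 2 sites = 60. Section 9.2 states "With an attrition rate of 10%, a sample size of 30 dyads per arm will produce a 2-sided 95% confidence interval" with a width of 0.4 SD at SD = 1. With 10% attrition, 30 × 0.9 = 27 per arm, or 54 in all. The stated precision is recovered as t(0.975, 26)/√27 = 2.056/5.196 = 0.396 SD. The smallest n with this quantity at or below 0.4 is 27, and 27/0.9 = 30. This works only if width is read as the half-width for one arm's mean. Nothing below depends on that reading; the calculation serves to confirm 54 as the planning figure. Voluntary completion can lower it.

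**2. Refitting at each visit.** The usual component score for person i at visit k is s(i,k) = Σⱼ w(j,k) · [x(i,j,k) − m(j,k)] / d(j,k), where m and d are the sample mean and SD of subscale j at visit k. Summed over the people used in the fit, each bracket is zero, so the mean score is zero at each visit. Among the same completers, pooled mean change = 0 − 0 = 0 whatever the true change. With equal arms the two arm means would then be mirror images about zero.

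For contrast, freeze the baseline centring, scaling and weights. Assume p subscales with equal correlation r and a true improvement of 0.5 SD on each. The expected change, in SDs of the baseline component, is 0.5√p / √(1 + (p − 1)r).

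- p = 3, r = 0.6: 0.866/√2.2 = 0.58
- p = 6, r = 0.2: 1.225/√2 = 0.87

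Simulation with n = 54, p from 3 to 6 and r from 0.2 to 0.6 gave 0.59 to 0.82 with frozen weights and zero in every replicate with refitted scores. The median correlation between refitted and frozen change scores was 0.98 or higher, so the comparison between arms would largely survive. The before-after change would not.

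**3. Stability of the weights.** The documents do not give the number of subscales or their correlation, so both are varied as assumptions. Each cell comes from 800 simulated samples from a one-factor model with mildly unequal loadings, keeping the first component of the subscales. Ranges are over 3, 4 and 6 subscales.

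| Average correlation | CV of a weight, n = 54 | Two pilots' scores, n = 54 | Two pilots' scores, n = 30 | Pilot score vs simple sum, n = 54 |
|---|---|---|---|---|
| 0.2 | 26–32% | 0.63–0.92 | 0.23–0.69 | 0.80–0.95 |
| 0.4 | 9–11% | 0.99 | 0.94–0.98 | 0.99 |
| 0.6 | 4–6% | >0.99 | >0.99 | >0.99 |

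The last three columns are 5th percentiles of the correlation between scores. Weights always differ from sample to sample, but the score they produce moves materially only when subscales correlate weakly.

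**The case against.** The best defence has four parts.

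- The text speaks of summary scores of the subscales, which presupposes the instrument's structure. The natural readings are one component within each subscale or one across subscale totals. Under an assumed structure of 24 items in four subscales correlated 0.5, both give 5th-percentile agreement between two pilots of about 0.99 at n = 54. This stands. At moderate correlation, component and sum scores nearly coincide.
- Weights can be frozen and item responses are retained, so the scale could be carried forward. This also stands. A reader might infer that the pilot's score cannot be used in the ePCT, or that so small a sample makes its weights meaningless. The documents support neither. The first overlooks freezing. The second needs weak correlations, or a rotated multi-component item analysis that the plan never describes.
- The plan does not say that the instrument's own scoring is abandoned, nor that components will be refitted at 3 months. Building scores first and then analysing change is compatible with a single weight set. That is fair, so the zero-change result is a consequence of one permitted reading and not of a stated procedure.
- Aim 2b is about the feasibility of measurement, and response rate and completion time do not depend on scoring. True, but section 9.4 also lists change in FCMAHS, and section 9.5 makes Aim 2b the aim with comparative intention-to-treat results.

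**Conclusion.** The point holds in limited form. The stated scoring method puts the FCMAHS change, SD and effect in units set by at most 60 care partners, and transfer to the ePCT is not assured because neither the weights nor a fixed score is specified in advance.

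The size depends on what the documents leave open. The effect on the score is small if subscales correlate about 0.4 or more and material if they correlate about 0.2. The zero pooled change follows exactly if scores are refitted and centred at each visit, and does not arise if baseline weights are frozen.

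Severity is minor: this is a secondary measure in a pilot that sets no statistical hypotheses. It is a free improvement, since fixed scoring loses almost nothing when correlations are moderate and protects the outcome when they are weak.

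**What to change.** In sections 9.1 and 9.5, make the instrument's fixed item-to-subscale and total scores, computed identically at baseline and 3 months, the main FCMAHS outcome in the regression. Write the scoring rule into the plan, since the present text does not give it. Keep principal components as an exploratory analysis, fitted once on baseline data, with the same centring, scaling and weights applied at 3 months, and state the input (items or subscale totals) and the number of components kept.

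The cost is a few sentences. The questionnaire, the data collected and the 60 dyads are unchanged.

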The proposed pragmatic intervention consists of the following strategies: 1) direct-toconsumer deprescribing educational materials designed to activate the care partner and PLWD; 2) a telehealth visit in which a clinical pharmacist discusses benefits and harms of the patient's medications with the patient and care partner in the context of their goals and preferences; and 3) pharmacist-PCP communication in which the pharmacist provides tailored deprescribing recommendations designed to be useful and actionable for the PCP. The study will assess the feasibility and preliminary efficacy of the intervention in two healthcare systems, to guide the subsequent evaluation of the intervention in an ePCT.

We will enroll 60 patients and their care partners as dyads (15 dyads per arm at each site). Patient eligibility criteria will be: age \geq 65 years with a diagnosis of ADRD from ICD-9 or ICD-10 visit codes or from the EHR problem list and \geq 5 chronic medications. In

Baltimore, the study site will be 1-4 clinics that are part of Johns Hopkins Community Physicians (JHCP). In Denver, the study sites will be KPCO greater Denver metro primary care practices. Dyads at each pilot site will be randomly assigned to receive the pharmacistled intervention immediately after the educational mailing or to a delayed intervention control group that will receive the pharmacist-led component 3 months after the mailing. (Please see the Consent section for a discussion of consent options for consenting patients as part of pragmatic trials.)

This protocol employs a pragmatic design. The intervention is delivered by clinical pharmacists who are already integrated in primary care clinics at JHCP and KPCO. The pharmacists are trained in complex geriatric medication management and routinely provide comprehensive medication management to Medicare beneficiaries.

Aim 1 is to assess the feasibility and acceptability of ALIGN in two different health care systems, to guide the subsequent evaluation of the effectiveness of the intervention in an ePCT. Data to measure feasibility will be acquired from the EHR, checklists completed by the pharmacists, and audiorecordings of pharmacist phone calls with care partners. We will collect the following measures:

• Proportion of dyads that opt out of the intervention;

• Proportion of pharmacist messages to the PCP that receive an acknowledgement or response;

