6.2.1 Screening Evaluation Consenting Procedure

As described in section 4.3, initial eligibility will be determined based on available clinical and claims data under a waiver of HIPAA Authorization.

Project assistants will serve as scheduling coordinators for the pilot study. Dyads who do not opt out (and those who opt in) will be called by the project assistant approximately 14 days after the study materials are mailed. Using the same approach that clinic staff use to call patients with dementia on the phone and identify their care partners during the course of clinical care, the project assistant will use an IRB-approved script (attached) to describe the pharmacist consult and assess interest. If the patient declines to identify a care partner and does not have a care partner listed in the EHR, the dyad will not be eligible. This phone call is described in section 4.3.

Participation in the pharmacist consult is not contingent on completion of the secondary outcome measure, FCMAHS. After scheduling the pharmacist consult, project assistants will offer care partners the option of completing the FCMAHS. They will obtain verbal consent for the FCMAHS when administering it over the phone (see script). If the care partner cannot complete the FCMAHS over the phone during the scheduling phone call,

the project assistant will offer to call back before the pharmacist visit (up to 28 days) or to later e-mail them a link to an electronic version.

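### The plan does not say whether multiple imputation and health-system handling cover FCMAHS, so the Aim 2b intention-to-treat comparison defaults to care partners with both scores

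*Combined protocol and SAP*

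**What the plan says.** Sections 9.1 and 9.5 carry the same analysis text. For Aim 2b they state: "In Aim 2b, the primary analyses will rely on intention-to-treat analysis". The paragraph on pMRCI specifies a change-score regression and accounts for clustering by health system through robust standard errors. It ends: "We will use multiple imputation to account for missing data". The FCMAHS paragraph comes next. It builds summary scores by principal components and continues: "We will then analyze changes in FCMAHS before and after intervention", with a linear regression of the change scores on assignment. It gives no analysis set, missing-data method or site handling.

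How FCMAHS is collected:

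- Section 6.2.1: "Participation in the pharmacist consult is not contingent on completion of the secondary outcome measure, FCMAHS".
- Sections 6.2.2 and 9.2.1: randomisation precedes the call at which FCMAHS is offered.
- Section 6.2.3: the 3-month measure goes only to care partners who chose to complete it.
- Section 6.2.4: after early discontinuation, record data are still extracted but FCMAHS is not offered.

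Section 3 randomises dyads at each site, with a target of "15 dyads per arm at each site". Section 6.1 schedules pMRCI and chronic medication count at both time points.

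**The concern.** A change score needs both values. With no missing-data rule, a linear regression drops every dyad that lacks either one. FCMAHS depends on a voluntary response at two time points, whereas pMRCI comes from records that are extracted even after early discontinuation. By paragraph structure, the missing-data method sits with the outcome that does not depend on voluntary response.

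All FCMAHS non-response, including at baseline, occurs after randomisation. The protocol's timetable also allows it to differ by arm. The immediate arm has its pharmacist call within 4 weeks of enrolment; the delayed arm has it at 3 to 4 months, at or after the 3-month FCMAHS. The example of early discontinuation in Section 6.2.4 is opting out during that call, so the rule can remove follow-up scores mainly from the immediate arm.

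At stake are the Aim 2b arm difference and its variability, which the pilot is meant to pass on to the larger trial. If the reasons for answering differ by arm, a comparison of two-time responders no longer has the protection of randomisation. Leaving out health system is a separate and smaller matter. It bears on precision and on matching the allocation, not on whether the analysis is intention-to-treat.

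**Working it through.** **1. The plan's precision figure.** Section 9.2 gives 30 dyads per arm, 10% attrition and a two-sided 95% interval of width 0.4 SD, "when the SD of the study outcome (ie, based on normalized score) is 1". After attrition, 30 × 0.9 = 27 per arm. For one arm's mean the half-width is t(0.975, 26)/√27 = 2.056/5.196 = 0.396. The stated 0.4 is therefore recovered as a one-arm half-width. The FCMAHS comparison is between arms, and the 10% is not tied to FCMAHS response. How Section 9.2 words the width is a separate matter, and nothing below depends on it.

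**2. Precision if only complete pairs are used.** Half-width of the arm difference = t(0.975, 2n − 2) × √(2/n), with SD 1. The documents give no completion rate, so a range is assumed, equal in both arms:

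| Both scores present | n per arm | Half-width (SD) |
|---|---|---|
| 90% | 27 | 2.007 × 0.272 = 0.546 |
| 80% | 24 | 2.013 × 0.289 = 0.581 |
| 70% | 21 | 2.021 × 0.309 = 0.624 |
| 60% | 18 | 2.032 × 0.333 = 0.677 |
| 50% | 15 | 2.048 × 0.365 = 0.748 |

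**3. Bias when selection differs by arm.** Every input here is an assumption. A standardised record-based variable has slope 0.4 on FCMAHS change. The log-odds of response are 0.85 + g × variable, giving about 68% to 70% response. There is no true effect. Shift = 0.4 × (mean of the variable among responders in one arm − the same mean in the other).

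The responder mean is 0.118 for g = 0.4 (odds ratio 1.5 per SD), 0.228 for g = 0.8 (odds ratio 2.2) and 0 for g = 0; a negative g reverses the sign.

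| Pattern of response | Shift (SD) |
|---|---|
| Same g in both arms | 0 |
| Same direction, g = 0.8 against 0.4 | 0.4 × (0.228 − 0.118) = 0.04 |
| One arm only, g = 0.4 | 0.4 × 0.118 = 0.05 |
| One arm only, g = 0.8 | 0.4 × 0.228 = 0.09 |
| Opposite directions, g = ±0.4 | 0.4 × 0.237 = 0.09 |
| Opposite directions, g = ±0.8 | 0.4 × 0.456 = 0.18 |

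In the opposite-direction rows the arms' odds ratios differ by a factor of 2.2 (g = ±0.4) or 5.0 (g = ±0.8), which is a strong assumption.

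**4. Bias when the amount missing differs by arm.** This is the route that Section 6.2.4 could open. Shift = d × (fraction missing in the immediate arm − fraction missing in the delayed arm), where d is the completer-minus-non-completer difference in mean change, taken as equal in both arms. With an assumed 30% against 10% missing, d = 0.25, 0.5 and 1 SD give 0.05, 0.10 and 0.20 SD. Equal missingness gives zero.

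**The case against.** A reader might infer that the plan commits to a complete-case analysis of FCMAHS. It does not. The imputation sentence names no outcome and may be meant for both, and the opening paragraph of Section 9.5 separates missing follow-up from non-compliance. Complete cases are what the FCMAHS paragraph yields if nothing is added; they are not a stated choice.

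A reader might also infer that pMRCI has a health-system model term that FCMAHS lacks. The plan has only a robust standard-error adjustment. Copying it across would not help, because cluster-robust errors are unreliable with two systems. A fixed term for FCMAHS beside robust errors for pMRCI would leave the two models inconsistent, so they are best considered together.

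Nor can pMRCI be assumed nearly complete. Its availability is an Aim 2a question, and Section 6.2 says the extraction algorithm is still being adapted. Imputation is not misplaced there, and the auxiliary variables may themselves have gaps.

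The largest bias figures rest on the strongest assumptions, and 0.18 SD is still under a third of 0.62 SD (0.18/0.62 = 0.29). Imputation removes bias only so far as observed variables explain response.

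The stakes are modest: the pilot has no statistical hypotheses, and FCMAHS response rate is itself a result. Imputing for every randomised dyad would also go too far, since Section 4.3 excludes patients without a care partner at a call made after randomisation.

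All of this limits the point. None of it supplies the missing statement for the one aim that claims intention-to-treat.

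**Conclusion.** The point holds as a gap in the specification. Sections 9.1 and 9.5 do not say that imputation or health-system handling applies to FCMAHS. By default the Aim 2b regression uses only care partners with both scores and ignores health system, although dyads are allocated within each site. That default does not match the intention-to-treat claim, and Section 6.2.4 widens the mismatch by withholding the measure from some randomised dyads.

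The size of any bias cannot be derived from the documents. Under the assumed response model it runs from zero, through about 0.05 to 0.09 SD with selection in one arm only, to about 0.18 SD with selection in opposite directions. Unequal missingness gives similar values and reaches 0.20 SD only if completers and non-completers differ by a full SD. All are small beside a half-width of about 0.62 SD at 21 pairs per arm. The pilot stays valid. The correction is worth making because it is cheap and these estimates are meant to inform the larger trial.

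**What to change.** In the FCMAHS paragraph of Sections 9.1 and 9.5:

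- Include health system as a fixed term in the change-score regression.
- State that multiple imputation covers FCMAHS for all randomised dyads with an identified care partner. Keep the model short: arm, health system, FCMAHS summary scores at both visits, and pMRCI or chronic medication count where available.
- Report FCMAHS completion by arm, and present the complete-case analysis as a sensitivity analysis.
- Reconcile the Section 6.2.4 rule on not offering FCMAHS after early discontinuation with the intention-to-treat statement.

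The analysis wording needs no new data: pMRCI and medication count are already scheduled at both time points. The cost is a few sentences and slightly more analysis work. The imputation model must stay small at about 30 dyads per arm, and it corrects only for what the observed variables explain.
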